7.3.1.2 Participating Sites

Participating sites are responsible for reporting adverse events to their IRB according to its specific requirements and to the Coordinating Center as follows:

Fatal Events whether anticipated or unanticipated, and whether or not related to the study must be reported to the Coordinating Center within **24 hours** of the participating site Principal Investigator's learning of the event.

Serious and Unanticipated Adverse Events as defined above must be reported to the Coordinating Center within **24 hours** of the participating site Principal Investigator's learning of the event.

Other Serious Adverse Events which may result in a change to the protocol, informed consent, or risk to subjects as specified in the protocol must be reported within **three (3) working days** of the participating site Principal Investigator's learning of the event.

Adverse Events which result in no change to protocol, informed consent, or risk to subjects must be reported to the Coordinating Center on a monthly basis.

Adverse event reports are to be faxed or e-mailed to the Coordinating Center Study Coordinator. Follow-up reports are faxed, mailed, or sent electronically to the Coordinating Center as necessary.

The investigator must also report follow-up information about SAEs within the same time frames.

If a non-serious AE becomes serious, this and other relevant follow-up information must also be provided within the same time frames described above.

All SAEs must be collected whether or not they are considered causally related to the investigational product. Investigators and other site personnel are responsible for reporting all causally related SAEs to their IRB and the Protocol Chair.

8. STUDY CALENDAR

Note that the study calendar is based on the ideal subject. The schedule should be followed as closely as realistically possible, but may be modified due to problems such as scheduling delays, conflicts such as clinic closure or poor weather conditions, or other unforeseeable events.

	Pre-Study ¹	SBRT ^{3,9}	Follow-up (in time Post-RT)									
			4 weeks (± 7 days)	3 mo ⁶	6 mo ⁶	9 mo ⁶	12 mo ⁶	18 mo ⁷	24 mo ⁷	30 mo ⁷	36 mo ⁷	
Informed Consent	X											
Demographics	X											Follow for survival
Medical History	X											
Physical Exam	X		X	X	X	X	X	X	X	X	X	
Height	X											
Weight & Vitals	X	X	X	X	X	X	X	X	X	X	X	
Performance Status	X	X	X	X	X	X	X	X	X	X	X	
Biopsy-confirmed sarcoma	X											
Treatment planning scan	X											
CBC w/ diff, plts, CMP	X ₄		X	X	X	X	X	X	X	X	X	
CT of treatment site	X ₈			X	X	X	X	X	X	X	X	
MRI	X ₅			X ₁₁	X ₁₁	X ₁₁	X ₁₁	X ₁₁	X ₁₁	X ₁₁	X ₁₁	
FDG-PET (optional)	X			X ₁₁	X ₁₁	X ₁₁	X ₁₁	X ₁₁	X ₁₁	X ₁₁	X ₁₁	
Tumor measurements	X			X	X	X	X	X	X	X	X	
Pregnancy test ²	X											
Pain Assessments ¹⁰	X	X	X	X	X	X	X	X	X	X	X	
Toxicity Assessment		X	X	X	X	X	X	X	X	X	X	

¹Pre-SBRT assessments should be performed within 4 weeks of radiation treatment

²Pregnancy test by urine or serum, for women who are not post-menopausal as defined in Appendix A

³ Patients will receive SBRT over a five-day period. Ideally all 5 fractions should be delivered Monday through Friday, however it may be delivered over two weeks
⁴ Within 1 week prior to radiotherapy
⁵ Optional depending on treatment site
⁶ Follow-up should occur +/- 14 days
⁷ Follow-up should occur +/- 30 days
⁸ CT scan must be performed within 4 weeks prior to the start of therapy, not required if MRI is obtained.
⁹ Patients will be able to receive chemotherapy 2 weeks after the completion of SBRT.
¹⁰ Brief Pain Inventory (Appendix C) and 10 point Visual Analog Scale (Appendix F); given the age population, the completion of these assessments may not be possible and therefore are optional for subjects under 18 years of age
¹¹ Follow-up PET/CT and MRI are at the discretion of the treating physician and are optional

9. MEASUREMENT OF EFFECT

9.1 Antitumor Effect – Solid Tumors

For the purposes of this study, patients should be re-evaluated for response 4 weeks after the initial treatment, every 3 months for the first year, and every 6 months for the second and third year.

9.1.1 Definitions

Evaluable for toxicity. All patients will be evaluable for toxicity from the time of their first treatment with SBRT.

Evaluable for objective response. Only those patients who have measurable disease present at baseline, have completed all fractions of SBRT, and have had their disease re-evaluated will be considered evaluable for response. These patients will have their response classified according to the definitions stated below. (Note: Patients who exhibit objective disease progression prior to the end of SBRT will also be considered evaluable.) Evaluable patients will also be those who received the protocol-specified dose.

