5.8 Criteria for Removal from Study

Patients will be removed from study when any of the criteria listed in Section 5.5 applies. The reason for study removal and the date the patient was removed must be documented in the Case Report Form.

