6. DOSE MODIFICATIONS

In young children less than 10 years of age where the study dose is not considered safe to deliver as a result of the radiation dose that will be delivered to surrounding normal tissues, a dose of 3500 cGy delivered in 700 cGy fractions in 5 fractions every day to the GTV, will be allowed as a prescription dose. A dose modification may be made at the discretion of the treating physician but the Principal Investigator must be informed and approve this change.

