13.4 Reporting and Exclusions

13.4.1 Evaluation of toxicity. All patients will be evaluable for toxicity from the time of their first treatment with SBRT.

13.4.2 Evaluation of response. All patients included in the study must be assessed for response to treatment, even if there are major protocol treatment deviations. Each patient will be assigned one of the following categories: 1) complete response, 2) stable disease, 3) progressive disease, 4) early death from malignant disease (defined as death prior to first evaluation after completion of SBRT), 5) early death from toxicity, 6) early death because of other cause, or 9) unknown (not assessable, insufficient data). [Note: By arbitrary convention, category 9 usually designates the “unknown” status of any type of data in a clinical database.]

All of the patients who were enrolled on the trial should be included in the main analysis of local control.

All conclusions should be based on all enrolled subjects. Sub-analyses may then be performed on the basis of a subset of patients, excluding those for whom major protocol deviations have been identified (e.g., early death due to other reasons, early discontinuation of treatment, major protocol violations, etc.). However, these sub-analyses may not serve as the basis for drawing conclusions concerning treatment efficacy, and the reasons for excluding patients from the analysis should be clearly reported. The reason for performing subset analyses would be to generate hypotheses for future prospective clinical trials.

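### Section 9.1.1 classifies response only in patients who finish SBRT and are re-evaluated, 13.4.2 requires everyone to be assessed and counted, and no rule says how unassessable patients count in the 5-of-6 and 17-of-20 decisions

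*Combined protocol and SAP*

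**What the plan says.** **Section 9.1.1 (Definitions).** Evaluable for objective response are "Only those patients who have measurable disease present at baseline, have completed all fractions of SBRT, and have had their disease re-evaluated". The section goes on: "These patients will have their response classified according to the definitions stated below". It makes one exception: "Patients who exhibit objective disease progression prior to the end of SBRT will also be considered evaluable". It then adds a sentence on dose: "Evaluable patients will also be those who received the protocol-specified dose".

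**Section 13.4.2 (under Reporting and Exclusions).** The rule here is: "All patients included in the study must be assessed for response to treatment, even if there are major protocol treatment deviations". Patients are sorted into categories: complete response (1), stable disease (2), progressive disease (3), early death from malignancy, toxicity or other cause (4-6), or unknown (9). For the primary endpoint: "All of the patients who were enrolled on the trial should be included in the main analysis of local control". Sub-analyses that leave out patients with major deviations are allowed, but may not support efficacy conclusions.

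**Sections 13.1.2 and 9.1.4.1.** Local control is the absence of progression, so CR and SD both count. SD is the residual class: a patient who meets neither the CR nor the PD criteria.

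**Section 13.2.** Simon optimal two-stage design. Stop if 4 or fewer of the first 6 respond; call the regimen promising if 17 or more of 20 respond. Enrolment is set at 20, with no allowance for patients who cannot be assessed.

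**Section 6.** For some children under 10, a reduced dose "will be allowed as a prescription dose".

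**The concern.** The two sections give different answers to the question of who receives a response class, and the primary endpoint is made from response classes. A patient who stops SBRT early without progression, or who is never re-imaged, has no class under 9.1.1 but must be categorised and counted under 13.4.2.

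Such patients are foreseeable. Section 5.5 lists intercurrent illness, unacceptable adverse events and withdrawal as reasons to stop, and Section 5.8 says: "Patients will be removed from study when any of the criteria listed in Section 5.5 applies". A 6-month assessment of the treated site may then be missing.

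Section 13.4.2 places these patients in the analysis but does not say how they score. Three treatments can be argued from the text:

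- **Not controlled:** categories 4-6 and 9 are listed apart from CR and SD.
- **Controlled:** no progression was documented, and SD takes in whatever is neither CR nor PD.
- **Excluded:** this is the effect of 9.1.1.

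In an open single-arm trial of 20 patients, that choice could be made with the outcomes in view. Excluding early deaths and unscanned patients also selects those who tolerated treatment and reached a scan.

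The dose sentence in 9.1.1 adds a smaller ambiguity. It can be read as a further restriction or as an addition, and it does not say whether the Section 6 reduced dose is protocol-specified.

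**Working it through.** **Inputs.** From 13.1.2 and 13.2: null rate 0.70, anticipated rate 0.90, n1 = 6 (stop at 4 or fewer), N = 20 (promising at 17 or more). The documents give no unassessable fraction *d*; 5% and 10% are assumptions.

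**1. The plan's own figures.**

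P(early stop) = P(Bin(6, p) ≤ 4), which is 0.580 at p = 0.70 and 0.114 at p = 0.90. The plan states 58% and 11%.

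P(promising) = P(X1 = 5) × P(Bin(14, p) ≥ 12) + P(X1 = 6) × P(Bin(14, p) ≥ 11).

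- p = 0.70: 0.3025 × 0.1608 + 0.1176 × 0.3552 = 0.0904
- p = 0.90: 0.3543 × 0.8416 + 0.5314 × 0.9559 = 0.806

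The type I error is 9.0% and the power 80.6%, within the stated 10% and 20% limits. The exact 90% interval for 18/20 is (0.717, 0.982), as the plan gives it. The design is correctly computed, on the premise that every patient has a 6-month outcome.

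**2. Reported rate for the same data (assumed counts, exact 90% CI).**

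| Controlled | Unassessable | All 20 enrolled | Evaluable only |
|---|---|---|---|
| 17 | 2 | 17/20 = 85% (0.66-0.96) | 17/18 = 94% (0.76-1.00) |
| 16 | 2 | 16/20 = 80% (0.60-0.93) | 16/18 = 89% (0.69-0.98) |

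In the first row the lower limit moves from below 70% to above it. The responder count is the same in both columns.

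**3. Decision rule, unassessability unrelated to outcome.**

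Counted as controlled, the effective rate is d + p(1 − d). Counted as failures, it is p(1 − d). Putting these into the formula in step 1:

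| d | Controlled: rate at null | Type I error | Failure: rate at null | Type I error | Failure: rate at 0.90 | Power |
|---|---|---|---|---|---|---|
| 0 | 0.700 | 9.0% | 0.700 | 9.0% | 0.900 | 80.6% |
| 5% | 0.715 | 11.5% | 0.665 | 4.9% | 0.855 | 60.4% |
| 10% | 0.730 | 14.5% | 0.630 | 2.5% | 0.810 | 40.0% |

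**4. Exclusion without replacement.** Both rules count responders against fixed numbers. Dropping an unassessable patient removes no responder, so with 6 and 20 enrolled the decision is the same as if that patient were a failure. Only the reported rate and interval change, as in step 2.

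**5. Exclusion with replacement, all unassessable patients being failures.** With an all-enrolled rate of 0.70, control among the evaluable is 0.70/(1 − d): 0.737, 0.778 and 0.824 at d = 5%, 10% and 15%. P(promising) is then 16.0%, 27.7% and 45.9%. If instead unassessability is unrelated to outcome, the rate among the evaluable stays 0.70 and the error stays 9.0%, even with replacement.

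**The case against.** The strongest reply is that 13.4.2 already settles the primary analysis. It sits in the statistical section, names the main analysis of local control, includes everyone enrolled, and bars efficacy conclusions from subsets. Section 9.1.1 defines evaluability for objective response and sets no denominator for local control. An analyst who dropped patients would be going against explicit text. This stands for the denominator.

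It does not settle the scoring. Categories 4-6 and 9 are listed apart from CR and SD, and 13.2 defines a responder as having control at 6 months, so non-responder is the more natural reading. But it is not stated, and the residual definition of SD leaves the other reading open, chiefly for category 9.

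A reader might infer that 9.1.1 breaks the 10% error and pushes it to 16-46%. The documents do not support that. Those figures need unassessable patients to be replaced and all of them to be failures. No section provides for replacement, and 13.2 counts patients, not evaluable patients.

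A reader might also infer that 9.1.1 discards everyone who stops early. It keeps patients who progress before SBRT ends. What it leaves out is early stoppers without progression, early deaths before any re-evaluation, and patients never re-imaged.

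On dose, 13.4.2 counts the Section 6 patients under either reading of 9.1.1, so for the primary analysis this is a point of wording.

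**Conclusion.** The contradiction is real and bears on the primary endpoint, because 13.1.2 uses the classes that 9.1.1 restricts and nothing confines 9.1.1 to a supportive analysis. Section 13.4.2 should be taken as governing the denominator. What is missing is a scoring rule for categories 4-6 and 9.

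At an assumed 5-10% unassessable, unrelated to outcome, the open choice is between an error of 11.5-14.5% (scored as controlled) and a power of 60-40% (scored as failures, with the error below 10%). Excluding these patients without replacement changes no go/no-go decision, but can move a reported 85% to 94%. The sizes depend on the assumed fraction and on independence from outcome; the existence of the gap does not. The sample size arithmetic itself is sound. Severity: should fix.

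**What to change.** 1. **9.1.1:** limit the evaluability restriction to the exploratory sub-analyses that 13.4.2 permits, and say that it does not govern the primary analysis.
2. **13.1.2 and 13.2:** state that the 6 and the 20 are all enrolled patients, without replacement, and that patients in 13.4.2 categories 3-6 and 9 are not responders at 6 months.
3. **9.1.1 and Section 6:** reconcile the protocol-specified-dose sentence with the permitted dose modification, so that patients treated under Section 6 stay in the main analysis as 13.4.2 requires.
4. **Reporting:** give the completers-only rate as a sensitivity analysis, with the number and reasons for those left out.

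The cost is a few sentences and one more line of results. The reported rate may be slightly less favourable, and power falls if patients cannot be assessed (step 3 of the working), which is a reason to obtain the 6-month treated-site assessment wherever possible.

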9.1.2 Disease Parameters

Measurable disease. Measurable lesions are defined as those that can be accurately measured in at least one dimension (longest diameter to be recorded) as ≥ 10 mm with diagnostic techniques (CT, FDG-PET/CT, or MRI). All tumor measurements must be recorded in millimeters (or decimal fractions of centimeters).

Non-measurable disease. All other lesions (or sites of disease), including small lesions (longest diameter < 10 mm with diagnostic techniques), are considered non-measurable disease. Leptomeningeal disease, ascites, pleural/pericardial effusions, lymphangitis cutis/pulmonis, inflammatory breast disease, abdominal masses (not followed by CT or MRI), and cystic lesions are all non-measurable.

Target lesions. Target lesions in this study will be considered metastatic sites up to a maximum of 5 lesions per patient. They should be recorded and measured at baseline. Target lesions should be larger than 10 mm in the smallest crosssectional diameter on CT or MRI and/or any lesion that shows increase metabolic uptake on FDG-PET/CT scans.

Non-target lesions. N/A

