3. PATIENT SELECTION

3.1 Inclusion Criteria

- 3.1.1 Patients must have histologically or cytologically confirmed nonrhabdomyosarcoma of soft tissue or bone at any site
- 3.1.2 Patients must have measurable disease, defined as at least one lesion that can be accurately measured in at least one dimension (longest diameter to be recorded) as ≥ 20 mm with conventional techniques or as ≥ 10 mm with spiral CT scan within 4 weeks of treatment start. See Section 9.1.3 for the evaluation of measurable disease.
- 3.1.3 Greatest tumor dimension of all sites must be ≤ 5.0 cm or <250 cm^3
- 3.1.4 There is at least 1 metastatic site at one or more of the following sites: spine or non-spine bone and at maximum 5 sites can be treated on protocol
- 3.1.5 Surgically unresectable site as determined by tumor board or surgeon or patients who decline surgery.
- 3.1.6 Patients must be greater than 3 years of age and ≤ 40 years of age.
- 3.1.7 Life expectancy of at least 9 months
- 3.1.8 Lansky performance status ≥ 50 (See Appendix E)
- 3.1.9 Ability to understand and the willingness to sign a written informed consent document and if a minor, have a guardian who meets the above criteria.

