9.1.3 Methods for Evaluation of Measurable Disease

All measurements should be taken and recorded in metric notation using a ruler or calipers. All baseline evaluations should be performed as closely as possible to the beginning of treatment and never more than 4 weeks before the beginning of the treatment.

The same method of assessment and the same technique should be used to characterize each identified and reported lesion at baseline and during follow-up. Imaging-based evaluation is preferred to evaluation by clinical examination when both methods have been used to assess the antitumor effect of a treatment.

Conventional CT, FDG-PET/CT, and MRI These techniques should be performed with cuts of 10 mm or less in slice thickness contiguously. Spiral CT should be performed using a 5 mm contiguous reconstruction algorithm. This applies to tumors of the chest, abdomen, and pelvis. Head and neck tumors and those of extremities usually require specific protocols.

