9.1.4 Response Criteria

9.1.4.1 Response Assessment of Bone Metastases

Radiographic assessment of bone metastasis can be difficult as remodeling bone may lead to residual abnormalities on bone scan, CT scan, and MRI scan. This leads to inherent difficulties in using RECIST 1.1 criteria for response assessment. For the purposes of the current protocol, response at bone metastasis will be graded as follows:

Complete response (CR) = A negative FDG-PET at the irradiated lesion in patients who have a positive FDG-PET at the time of SBRT at the target lesion. FDG-PET is optional on study. Therefore, CR will be recorded but not required to constitute a response.

Progressive disease (PD) = Any of the following will constitute PD:

- Development of a new soft tissue mass ≥ 1 cm in maximum axial dimension at a previous site of bone metastasis without a soft tissue component or with a soft tissue component < 1 cm in maximum axial dimension on previous evaluations.
- For bone metastasis with a soft tissue component ≥ 1 cm in maximum axial dimension on previous evaluations, an increase in the longest axial diameter of the soft tissue component by $> 20\%$.
- A previous bone metastasis that was positive on FDG-PET, became negative with protocol therapy, and then becomes positive again should prompt concern

for progression at that site. Confirmatory testing is required to document progression at a previous site of bone metastasis. Together with return of FDG-PET uptake, MRI scan with documentation of an enhancing bone lesion will constitute adequate evidence to support progression at that site. Biopsy is strongly encouraged, but not required to confirm progression at a previous site of bone metastasis.

- Biopsy evidence of viable sarcoma at a previously radiated bone metastasis.

Stable disease (SD) = Patients not meeting either CR or PD criteria.

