9.1.6 Clinical Response Parameters

Progression-free survival (PFS) is defined is the time from starting treatment to the time of first documented tumor progression or death due to any cause, whichever occurs first. Death is considered as an event here. For subjects whose disease does not progress or who do not die, PFS will be censored at the time of the last visit.

Time to progression (TTP) is defined as the time from starting treatment to the time of first documented tumor progression. Subjects who do not progress will be censored at the time of the last contact. In addition, death from any cause will also be censored.

Overall survival (OS) is defined as the time from starting treatment until death due to any cause. For subjects who do not die, time to death will be censored at the time of last contact.

Local Control (LC) is defined as the time from starting treatment until local relapse is documented. The target lesion will be considered locally controlled if criteria for progression are not met, taking as reference the smallest measurements recorded since the treatment started.

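### Section 9.1.3 allows 10 mm cuts where local failure is judged at 1 cm and 20% growth, so small soft-tissue components can be misread in the primary endpoint

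*Combined protocol and SAP*

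**What the plan says.** Four passages of the combined protocol and SAP bear on this.

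- **Slice thickness (9.1.3).** For conventional CT, PET/CT and MRI: "These techniques should be performed with cuts of 10 mm or less in slice thickness contiguously". For spiral CT: "Spiral CT should be performed using a 5 mm contiguous reconstruction algorithm". The rule is scoped to chest, abdomen and pelvis, and then: "Head and neck tumors and those of extremities usually require specific protocols". No thickness is given for those sites.
- **Measurable disease (3.1.2 and 9.1.2).** Entry needs at least one lesion of "20 mm with conventional techniques or as ≥ 10 mm with spiral CT scan". Section 9.1.2 says "Measurable lesions are defined as those that can be accurately measured in at least one dimension (longest diameter to be recorded", and accepts 10 mm on any of CT, PET/CT or MRI. For target lesions it adds "Target lesions should be larger than 10 mm in the smallest crosssectional diameter on CT or MRI", or FDG uptake.
- **Local failure (9.1.4.1).** Two of the four routes to progression are size-based. One is a new soft-tissue mass of at least 1 cm where the component was absent or below 1 cm before. The other, for a component already at least 1 cm, is "an increase in the longest axial diameter of the soft tissue component by" more than 20%.
- **Use in the endpoint (9.1.6 and 13.1.2).** Local control is judged "taking as reference the smallest measurements recorded since the treatment started". Section 13.1.2 defines the primary endpoint as absence of progression under 9.1.4.1.

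**The concern.** The coarsest permitted cut equals the failure threshold. A slice as thick as the mass being judged blurs its edge, and the reading then depends on where the slice falls. Errors go both ways: a new mass just over 1 cm can be read as under it, and an unchanged mass can appear to cross 1 cm or to grow by more than 20%.

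The permission matters in practice because MRI may replace CT at baseline (5.1 and the study calendar) and is required for spinal lesions (5.1, 5.2). The 20 mm minimum without spiral CT in 3.1.2 guards against this at entry. However, it applies to at least one lesion, while up to five may be treated, and 9.1.2 does not repeat it.

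The misread outcomes would enter a decision that needs 5 of 6 and then 17 of 20 patients controlled (13.2), where one patient can change the result.

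**Working it through.** **The plan's own figures.** The plan gives no measurement-error figure. Its two-stage design reproduces. Early stopping at 70% control is 1 − 0.7⁶ − 6·0.7⁵·0.3 = 1 − 0.1176 − 0.3025 = 0.580. At 90% it is 1 − 0.5314 − 0.3543 = 0.114. Section 13.2 states 58% and 11%.

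**Inputs.** Cut thickness T = 10 or 5 mm (9.1.3); thresholds of 10 mm and more than 20% (9.1.4.1). Assumed: a spherical mass of true diameter D; an edge seen where the mass fills at least half the slice thickness; contiguous slices at random position; the largest slice reading taken.

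**Formula.** Let d be the distance from the sphere's centre to the centre of the slice containing it, uniform from 0 to T/2. Half-filling requires a half-chord of at least max(d, T/4). The reading is therefore √(D² − 4·max(d, T/4)²), which ranges from √(D² − T²) to √(D² − T²/4).

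**Worked case, D = 12, T = 10.** Readings run from √44 = 6.6 to √119 = 10.9 mm. A reading of 10 mm or more needs d² ≤ (144 − 100)/4 = 11, so d ≤ 3.317, with probability 3.317/5 = 0.663. An unchanged mass reads below 10 mm and then at least 10 mm with probability 0.337 × 0.663 = 0.22. For D = 13, d ≤ √17.25 = 4.153, giving 0.831 and 0.169 × 0.831 = 0.14.

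| T (mm) | True D (mm) | Range of readings (mm) | Reads ≥ 10 mm | Falsely crosses 1 cm | False growth > 20% from a reading ≥ 10 mm |
|---|---|---|---|---|---|
| 10 | 11 | 4.6–9.8 | 0% | 0% | 0% |
| 10 | 12 | 6.6–10.9 | 66% | 22% | 0% |
| 10 | 13 | 8.3–12.0 | 83% | 14% | 0% |
| 10 | 14 | 9.8–13.1 | 98% | 2% | 6% |
| 10 | 15 | 11.2–14.1 | 100% | 0% | 4% |
| 10 | 20 | 17.3–19.4 | 100% | 0% | 0% |
| 5 | 11 | 9.8–10.7 | 92% | 8% | 0% |
| 5 | 12 | 10.9–11.7 | 100% | 0% | 0% |
| 5 | 15 | 14.1–14.8 | 100% | 0% | 0% |

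The last two columns are per pair of scans of an unchanged mass.

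**Where false progression is possible.** Crossing 1 cm needs √(D² − T²) < 10 ≤ √(D² − T²/4). On 10 mm cuts that is D from √125 = 11.2 to √200 = 14.1 mm; on 5 mm cuts, from √106.25 = 10.3 to √125 = 11.2 mm. False growth above 20% needs D² − T²/4 > 1.44(D² − T²), that is D < T·√(1.19/0.44) = 1.645·T. This is about 16.4 mm on 10 mm cuts. On 5 mm cuts it is 8.2 mm, below the 1 cm at which the rule starts.

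**Missed growth.** For a true 25% increase on 10 mm cuts from a qualifying first reading, the same model misses the 20% rule in about 25% of pairs at 12 mm, 12 to 13% at 15 mm, 4 to 5% at 20 mm and none at 30 mm. On 5 mm cuts none are missed from 12 to 30 mm.

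**The case against.** The case against has weight. Ten millimetres is a ceiling, not a target. Spiral CT is already held to 5 mm, CT is the scheduled follow-up scan, and follow-up MRI and PET are optional. Section 9.1.3 asks for the same technique throughout. The simulation CT has a recommended 1–3 mm thickness through the target (5.2), so a finer baseline image may exist. Section 3.1.2 still governs entry. Two of the four routes to progression (PET with MRI, and biopsy) use no diameter. All of this limits how often the problem can arise, but does not remove the permission. A site using MRI or conventional CT at 10 mm is within the plan, and extremity and head-and-neck sites have no stated limit.

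A reader might go further and infer that the plan has sites record only a whole-lesion diameter, so that soft-tissue growth is diluted and failures pass as control. The documents do not support that. Section 9.1.4.1 names the component, its axial dimension and the comparison with previous evaluations, and 13.1.2 points there. The wording in 9.1.2 sits inside a definition of measurable disease and does not limit sites to one number. The fields of the assessment forms are not in the documents. What remains is a missing explicit instruction to record the component.

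A reader might also want the effect on the chance of a false positive trial. That would need a miss rate, and the documents give none. Nor can an unchanged 12 mm mass trip the 20% rule on 10 mm cuts: from a qualifying 10 mm its reading can rise to at most 10.9 mm, about 9%. Its route to false progression is the 1 cm crossing.

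**Conclusion.** The point holds as a modest, inexpensive improvement to the measurement rules. Under the stated idealised assumptions, 10 mm cuts hide an 11 mm mass entirely and give false progression in about 22% to 4% of repeat pairs for unchanged masses of 12 to 15 mm. On 5 mm cuts the false progressions are zero in that range, with about 8% remaining at 11 mm. At 20 mm there is no false progression even on 10 mm cuts.

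The figures show direction and rough size, not observed error rates. They are per pair of scans. Taking the smallest of several earlier readings as reference, as 9.1.6 does, would raise the false-progression figures and is not counted. The documents do not say how many treated lesions will have components of this size or be read on cuts near 10 mm, so no trial-level error is claimed.

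**What to change.** - **9.1.3:** require contiguous cuts of 5 mm or thinner on every CT, PET/CT or MRI used to apply 9.1.4.1 to a treated site, wherever it lies. Leave other features of extremity and head-and-neck imaging to the site's own protocols.
- **3.1.2 and 9.1.2:** give one measurable-disease definition, with the same size and technique conditions in both.
- **Clarification only:** ask for the soft-tissue component's longest axial diameter (0 if none) for each treated lesion at baseline and at each scan, and state that 9.1.4.1 and the reference in 9.1.6 use that number.

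The cost is a reconstruction or acquisition setting on scans already scheduled, and one extra measurement per lesion per scan if the forms do not already hold it. Sample size and visit schedule are unchanged.
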